2.6.4 Other safety data

2.6.4.1 ECG and cardiac imaging data

The average triplicate values of 12-lead ECG results and the change in these results from the most recent dose will be summarized for each visit. The absolute value of QTcF will be plotted by box and whisker plot. The incidence of abnormal ECG (see [Table 5-5](#) in appendix) will be presented by treatment arm and by analysis visit and also in listing. The ECG finding will only be presented in listing.

Ambulatory Holter ECG will be recorded for 25 hours for all participants at randomization Day 1 for 25 hours, starting at least 1 hour before the start of the first infusion. Two kinds of device, Holter GI (Global Instrumentation) and Holter patch, will be used in different regions respectively. The abnormality findings from Holter for individual participant will be provided by listing, with the information of the date of first dose, the device type (GI or patch).

[figure not shown]
2.6.4.2 Vital signs

[figure not shown]
The change from baseline of vital signs (systolic/diastolic blood pressure, pulse rate, temperature) and weight will be summarized by treatment arm and by analysis visit, for Core Period up to 2 weeks' follow up visit, and separately for the Retreatment Period.

[figure not shown]
In addition, for systolic/diastolic blood pressure, the change from most recent dose will be summarized in a similar manner.

For Core Period up to 2 weeks follow up visit, the mean (SD) of change from baseline will be displayed by line plot. The change from the each dose up to 2 weeks will be plot in the same manner.

The proportion of any clinical relevant abnormality postbaseline and break donw by visit will be summarized and presented in listing at individual level.

2.6.4.6 Others

In case of cystitis or other lower urinary tract event, the PRO Bladder Pain/Interstitial Cystitis Symptom Score will be assessed. The PRO results will be presented in a listing.

The memory assessment will be performed to evaluate the present and absent of memory gap/amenia using orientation questions. The individual assessment results will be presented.

2.7 PK analyses

Variables

The following PK parameters will be determined using the actual recorded sampling times and non-compartmental method(s) with Phoenix WinNonlin (Version 8.0 or higher):

- Following first infusion in Core Period:
 - AUClast, Cmax, and Tmax will be determined from the plasma concentration-time data.
 - If data allow, secondary PK parameters will be estimated like T1/2, AUC0-t (t represent the end of the observation period of interest), AUCinf, CL, Vz (list of parameters are not limited).
- Following all other infusions in Core Period and all infusions in Relapse Retreatment Period:
 - PK samples will be collected at pre-dose (if scheduled), 40 min (end of infusion), and 4 h after end of infusion. The PK sample at the end of infusion (40 min) represents the Cmax and Tmax values. No other PK parameters will be estimated.

Descriptive analyses

All MIJ821 plasma concentrations and PK parameters including their descriptive statistics will be presented with three significant figures for Core Period and Relapse Retreatment Period. The exception will be %CV (Coefficient of Variation) values, which will be reported to one decimal place and N values, which will be reported as whole integers.

For the summary statistics of plasma concentration, the following time windows are defined: predose:

Table 2-11 Time window for plasma concentration

Nominal time after start of infusion	Elapsed time after start of infusion
0	All times before start of infusion
20 min	20 min +/- 2 min
40 min	40 min +/- 2 min
4 hours	4 hours +/- 30 min
24 hours	24 hours +/- 1 hour

Concentrations collected outside of the time windows will be not used for summary statistics of plasma concentrations. The time windows will be used for all infusions. For the PK parameter estimation, all concentrations with a recorded elapsed time will be used.

Summary statistics of plasma concentrations and PK parameters will be provided on separate tables and will include: mean (arithmetic and geometric), SD, CV (arithmetic and geometric), median, minimum and maximum, N value, by dose(/regimen) and study period. Concentrations below LLOQ (Lower Limit of Quantification) will be treated as zero in summary statistics and for PK parameter calculations. A geometric mean will not be reported if the dataset includes zero values. An exception to this is Tmax where median, minimum and maximum will be presented.

MIJ821 plasma concentrations will be expressed in mass per volume. Concentrations below the LLOQ will be reported as zero.

The plasma concentrations will be listed by

- study period, regimen, dose, subject, and visit/sampling time point

Overall descriptive summary statistics of plasma concentrations will be provided by

- study period, regimen, dose, and visit/sampling time point, including the frequency (n, %) of concentrations below the LLOQ, and
- study period, dose and visit/sampling time point, including the frequency (n, %) of concentrations below the LLOQ

PK parameters of each subject will be listed separately for the two dose regimens (one listing for repeated dosing, one listing for single dose) across Core and Retreatment dosing periods by:

- subject, dose, [REDACTED]
[REDACTED] visit

Overall descriptive summary statistics of PK parameters following the first infusion in Core Period will be presented by:

- regimen, dose
- dose (combined dose regimens)

Overall descriptive summary statistics of PK parameters following all other infusions in Core Period and all infusions in Relapse Retreatment Period will be presented by:

- study period, regimen, dose, and visit/sampling time point

Graphs

[figure not shown]
The following concentration-courses of MIJ821 in plasma will be generated:

[figure not shown]
- Summary plot – Core part (linear and semi-logarithmic view)
Arithmetic mean (SD) plasma concentration-time course per dose after first infusion across both dose regimens (overlying)

[figure not shown]
- Summary plot – Core part (linear and semi-logarithmic view)
Plasma concentration-time course per dose after first infusion across both dose regimens (spaghetti plot, individually per dose)
- Summary plot – Core part (linear and semi-logarithmic view)
Arithmetic mean (SD) plasma concentration-time course per dose and per dose regimen after first infusion (individually per dose)
- Summary plot – Core part (linear and semi-logarithmic view)
Plasma concentration-time course per dose and per dose regimen after first infusion (spaghetti plot, individually per dose)
- Summary plot – Core part (linear and semi-logarithmic view)
Arithmetic mean (SD) plasma concentration-time course per dose and dose regimens across all infusions (overlying)
- Summary plot – Retreatment (linear and semi-logarithmic view)
Arithmetic mean (SD) plasma concentration-time course per dose and dose regimen across all infusions (overlying)
- Individual plot (linear)
Plasma concentration-time course per individual across all infusions in Core and Retreatment study part

[figure not shown]
[REDACTED]

[figure not shown]
[REDACTED]

[figure not shown]

2.11 Interim analysis

One unblinded analysis will be performed when all participants completed Day 57 (2 weeks follow-up visit after the End of Core visit on Day 43). Data from Core Period will be analyzed according to the plan herein. The optimal dose will be identified based on the dose-response relationship established by MCP-Mod, as well the sustained efficacy effect, safety profile and PK of each MIJ821 dose and regimen compared to placebo.

This unblinded interim analysis will be conducted by study team. The individual level data will maintain blinded to investigators and participants until final database lock.

3 Sample size calculation

With the randomization ratio of 2:1:2:2:2 for the biweekly dosing arms, the sample size of 27:14:27:27:27 for placebo, MIJ821 0.0048 mg/kg, MIJ821 0.016 mg/kg, 0.048 mg/kg and 0.16 mg/kg, will provide about 80% power to detect a dose-response signal [to reject the null hypothesis of a flat dose-response curve where all MIJ821 dose means are equal to the placebo mean] for the biweekly dosing arms in change from baseline in MADRS at 24 hour using MCP-Mod methodology at the one-sided $\alpha = 0.05$ level. Since MIJ821 0.0048 mg/kg is

potentially non-effective, the sample size for this arm is chosen to be 50% of other arms and is sufficient for establishing the dose-response curve.

The 6 candidates DR curves (2 Emax, 4 Sigmoid Emax) for power calculation are defined in [Section 2.4.2.](#) [REDACTED]

[REDACTED]

For the two single infusion arms of 0.048 mg/kg and 0.16 mg/kg, to maintain the same precision as for the biweekly dosing arm vs placebo, 27 participants per arm are needed. In total the study needs 177 patients. Assuming a 10% dropout rate, approximately 195 pts in total (15 pts for 0.0048 mg/kg and 30 pts for the remaining 6 treatment arms) will be randomized.

All treatment arms (including both regimen) will be included in the MCP-Mod for the primary analysis which will provide about 92% power to detect a dose-response signal in change from baseline in MADRS at 24 hour using MCP-Mod at the one-sided 0.05 level.

4 Change to protocol specified analyses

Not applicable.

5 Appendix

5.1 Imputation rules

5.1.1 AE date imputation

[figure not shown]
Missing or incomplete dates will be listed as it is in any listings.

Incomplete or missing start date and end date of an adverse event will be imputed according to Novartis standards (details will be given in programming datasets specifications (PDS) document).

5.1.2 Concomitant medication/therapy date imputation

Incomplete or missing start date and end date of concomitant medication records will be imputed according to Novartis standards (details will be given in programming datasets specifications (PDS) document).

[REDACTED]

5.2 Rule of exclusion criteria of analysis sets

Table 5-2 Subject Classification

Analysis Set	PD ID that cause participants to be excluded	Non-PD criteria that cause participants to be excluded
FAS	NA	Not randomized No double-blind study drug taken
SAF	NA	No double-blind study drug taken
ENS	NA	Not enter into extension phase
RTS	NA	No retreatment administered No relapse observed None of responder or remitter
PKS	NA	Input from PK scientist

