### **12.5.2 Safety endpoints**

The safety and tolerability of MIJ821 will be evaluated by the number and severity of adverse events occurring during the first dose to 2 weeks post last dose of Core Period (or before retreatment if it's earlier than 2 weeks). For relapsed participants who take re-treatment of MIJ821, the safety and tolerability of retreatment will be evaluated by adverse events occurring from the start of retreatment to 2 weeks post last dose in Extension Period.

Clinical significant findings from laboratory test, physical examination, vital signs, 12-lead ECG, Holter ECG and additional safety scales will be reported as adverse events and analyzed as such.

For all safety analyses, the safety set will be used. All listings and tables will be presented by treatment group by Period.

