2.1.3 Analysis sets

The Randomized Set (RAS) consists of all randomized participants. The descriptions of population will be based on RAS.

The Full Analysis Set (FAS) comprises all randomized participants who received at least one dose of randomized study treatment. Participants will be analyzed according to the treatment they have been assigned to during the randomization procedure. The primary efficacy analysis for data in Core Period will utilize this analysis set.

The Safety Set (SAF) includes all participants who received at least one dose of study treatment. Participants will be analyzed according to the treatment received. In case participants take the wrong treatment (different with the assigned treatment), the first treatment received will be used in analysis. Safety analysis for data in Core Period will be based on SAF.

The Extension Set (ENS) is defined to include all subjects who joined Extension Period. Data collected during follow-up period will be analyzed based on ENS, and grouped by the assigned treatment in Core Period. In case participants take the wrong treatment during Core, the first actual treatment taken will be used for the analysis of safety data only. The analysis of data collected during extension period (before and after re-treatment period) will be based on ENS.

The Retreatment Set (RTS) is defined as a subset of SAF including participants who received at least one dose for the retreatment of relapse. Participants will be analyzed according to the treatment received for the first injection during the Retreatment Period. The efficacy and safety endpoints pertinent to Retreatment Period (see [Table 2-1](#)) will be analyzed based on RTS.

PK Analysis Set (PKS) includes all participants who provided at least one evaluable PK concentration. Determined PK concentrations may be excluded from the PKS (per the scientific judgement of the PK scientist, e.g. non-plausible concentrations). All subjects within the PK analysis set will be included in the PK data analysis. PK samples from subjects treated with MJJ821 will be measured and PK samples from placebo treated subjects will not be measured.

[REDACTED]

[REDACTED]

[REDACTED]

[REDACTED]

[REDACTED]

[REDACTED]

[REDACTED]

[illegible]

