2.3 Treatments (study treatment, rescue medication, concomitant therapies, compliance)

2.3.1 Study treatment / compliance

Descriptive statistics will be produced to describe the exposure to investigational product by treatment arm based on SAF, in terms of:

- the number of participants who received 1, 2 or 3 injections in Core Period. In addition for MIJ821 dose group, the number of injections with active MIJ821 dose will be counted.
- total duration of exposure, calculated by (last injection date – first injection date + 14) days: (for MIJ821 single infusion + 2 subsequent placebo infusions, the last dose date will count placebo infusion as well).

For each visit, the number and proportion of participants receiving study drug will be summarized. The dose change and reason, the duration of each infusion as well as interruption/discontinuation reasons (if applicable) will be listed.

The similar analyses will be provided for retreatment based on Retreatment Set (RTS).

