2.6 Safety analyses

The safety and tolerability of MIJ821 will be evaluated by adverse events, clinical significant findings from laboratory test, physical examination, vital signs, 12-lead ECG, holter ECG and safety scales.

Unless otherwise stated, the safety data listed in following subsections will be analyzed separately for Core Period based on SAF and Retreatment Period based on RTS. For the summary of change from baseline in Retreatment Period, the baseline will be the last valid assessment before retreatment, i.e. the baseline of retreatment.

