2.6.1 Adverse events (AEs)

Treatment-Emergent Adverse Events (TEAEs) are defined as adverse events starting or worsening after the first dose of study medication and up to 2 weeks post the last dose. For relapsed participants who receive retreatment of MIJ821 in Extension Period, adverse events starting after 2 weeks post the last dose of Core Period up to the start of retreatment will not be counted as TEAEs. The missing onset date of AE will be imputed before identify the TEAE (see imputation rule in [Appendix 5.1.1](#))

The Medical Dictionary for Regulatory Activities (MedDRA) version 24.0 or later will be used to code Adverse Event (AE) to a SOC and a PT.

TEAEs will be analyzed separately for Core Period and Retreatment Period:

- The summary of TEAEs in Core Period (up to 2 weeks post the last dose) will be based on SAF
- The summary of TEAEs in Retreatment Period (up to 2 weeks post the last dose of retreatment) will be based on RTS

The number (and percentage) of participants with TEAEs will be summarized by following approach as defined in [Table 2-7](#), in terms of all TEAEs, Treatment-Emergent Serious Adverse Events (TESAEs), TEAEs leading to treatment discontinuation, treatment-related TEAEs or TESAEs and death:

- by treatment, primary system organ class and preferred term
- by treatment, primary system organ class, preferred term and maximum severity
- by treatment, Standardized MedDRA Query (SMQ) and preferred term
- by treatment, preferred term with most frequent (incidence rate $\geq 5\%$)

Table 2-7 AE Summaries of Subject Incidence

Category	by SOC and PT	by SOC, PT and maximum severity	by most frequent PT (≥ 5%)
All TEAEs	Y	Y	Y
TESAEs	Y		
AEs leading to treatment discontinuation	Y		
Treatment-related TEAEs	Y		
Treatment-related SAEs	Y		
Deaths	Y		

For all AEs tables presented by SOC and PT (and grade), the SOC's will be presented in alphabetical order and PTs will be ordered within the SOC by decreasing order of frequency. AE tables by preferred term only will be sorted in descending order of frequency.

A participant with multiple adverse events within a primary system organ class is only counted once towards the total of the primary system organ class.

All AEs, deaths, SAEs and AEs leading to permanent study drug discontinuation will be listed separately.

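### SAP Table 5-2 adds relapse and responder/remitter conditions to the exposure-based Retreatment Set, so an infused participant could be left out of the retreatment safety and exposure summaries

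*SAP*

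**What the plan says.** SAP 2.1.3 states: "The Retreatment Set (RTS) is defined as a subset of SAF including participants who received at least one dose for the retreatment of relapse". Participants are grouped by the treatment received at the first retreatment infusion, and "The efficacy and safety endpoints pertinent to Retreatment Period" are assigned to this set.

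The safety sections follow that assignment. SAP 2.6 says safety data "will be analyzed separately for Core Period based on SAF and Retreatment Period based on RTS". SAP 2.6.1 adds: "The summary of TEAEs in Retreatment Period (up to 2 weeks post the last dose of retreatment) will be based on RTS". SAP 2.3.1 puts the retreatment exposure tables on the RTS, and SAP 2.2.1 does the same for completion or discontinuation of retreatment. The Extension Set covers the time around retreatment: "The analysis of data collected during extension period (before and after re-treatment period) will be based on ENS".

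Table 5-2 in SAP 5.2 then gives the rules for leaving each set. In the RTS row, the protocol-deviation column is not applicable, and the column of other criteria that cause exclusion reads "No retreatment administered No relapse observed None of responder or remitter".

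Protocol 12.5.2 says: "For all safety analyses, the safety set will be used". Protocol 12.1 defines that set by at least one dose received. SAP section 4 reports no change to the protocol's analyses.

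**The concern.** A set used for safety should be defined by exposure. Relapse and response status are efficacy conditions. If they also decide who is counted, a person who received the infusion can be missing from the tables meant to describe what happens after it. The people at risk of removal are those dosed outside the intended path or with incomplete records, which is where a safety summary should be most complete.

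Protocol 1.2 names the safety of repeated administration as one purpose of the Extension. Former placebo participants are a particular case. Under Protocol 6.3.2 they first receive active drug at retreatment, while the Core safety tables count them under placebo. If one of them were excluded from the RTS, that person's only active exposure would stand in no summary table under an active dose.

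**Working it through.** There is no figure to reproduce. The check is a comparison of the two RTS rules, followed by a search for any other summary that would pick up an excluded participant.

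**Step 1: how the Table 5-2 row reads.** The column holds criteria that cause exclusion, and SAP 2.2.1 points to this appendix as the exclusion rule. In the FAS row, not being randomized or not taking study drug is each enough alone. The natural reading of the RTS row is the same: any one of the three reasons removes the participant.

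**Step 2: apply both rules to someone who received a retreatment infusion.**

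| Participant infused at retreatment | SAP 2.1.3 | Table 5-2 |
|---|---|---|
| Responder or remitter at End of Core, relapse reported on the CRF | in | in |
| Responder or remitter, no relapse recorded on the CRF | in, on exposure | out |
| Neither responder nor remitter, dosed in error | in, on exposure | out |
| Day 43 MADRS missing | in, on exposure | out, if the missing-score rule applies |

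The second row rests on SAP 2.5.1, where relapse is the investigator's evaluation entered on a CRF form and participants with none reported are not counted. The last row rests on the rule in the same section that a missing score means not a responder, or not a remitter, at that timepoint. The SAP does not say that this rule also governs Table 5-2, so I take that as an assumption.

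**Step 3: look for another table that would catch them.**

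- SAP 2.1.1 defines the last dose to include retreatment, so an event within 2 weeks of a retreatment infusion is still treatment-emergent under SAP 2.6.1.
- The Core summary stops 2 weeks after the last Core dose.
- The retreatment summary is on the RTS.
- The Extension Set is described as covering the time before and after retreatment, not the retreatment period itself.
- The AESI and laboratory summaries for the Retreatment Period follow the SAP 2.6 default, which is the RTS.

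The event is therefore treatment-emergent by definition but falls in no treatment-emergent summary table.

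**Step 4: effect on a table.** Suppose r participants in a group are infused and e of them have the event. Of these, k are excluded by the extra conditions, and f of those k have the event. The table reports (e − f)/(r − k) instead of e/r. With k = 0 the two agree. The documents give neither r nor k.

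**Step 5: compare with the protocol.** Limiting retreatment tables to people who were retreated is a reasonable way to present the Safety Set by period. Removing some of the retreated on efficacy grounds is a further restriction. It is not in Protocol 12.1 or 12.5.2, and SAP section 4 does not record it.

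**The case against.** The strongest reply is that the RTS row only lists the ordinary reasons why a randomized participant is not in the set: never retreated, because there was no relapse or because the person was ineligible. The entry of not applicable under protocol deviations supports this, and the extracted table shows no and/or between the reasons. However, the column heading and SAP 2.2.1 both present the entries as exclusion rules, and having no listed deviation does not cancel the criteria in the next column. If the benign reading was intended, the two extra lines add nothing and can go.

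A second reply is that SAP 2.1.3 speaks of retreatment of relapse, and Protocol 12.5.2 describes retreatment safety for relapsed participants, so relapse is already implied. That has some force for the relapse condition. Neither text contains a responder or remitter condition, so the disagreement with Table 5-2 remains.

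A third reply stands in full: the data are not lost. SAP 2.6.1 lists all adverse events, deaths, serious events and events leading to discontinuation without limiting them to the RTS. SAP 2.6.1.1 and 2.6.2 add AESI and death listings. A reader might infer that these events would go unreported, but the documents do not support that.

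A reader might also infer that any retreatment outside the criteria in Protocol 3.4 leads to exclusion, such as MADRS visits too far apart or a non-remitting responder without the required worsening. That is not supported either. Relapse status comes from the investigator's CRF entry, not from a programmed check, so such participants would normally have a relapse reported. The second of these is a responder by definition.

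**Conclusion.** The inconsistency is real and minor. Table 5-2 narrows the RTS beyond its definition in SAP 2.1.3 and beyond the protocol's rule for safety analyses. Read as written, it removes certain infused participants from the retreatment exposure, adverse event and other safety summaries.

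This rests on two readings: that each Table 5-2 reason is sufficient alone, and, for the missing Day 43 score only, that the SAP 2.5.1 rule decides responder status here.

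The size cannot be estimated. The protocol offers retreatment only to relapsing responders or remitters, so the gap concerns dosing errors and record mismatches, and it may affect nobody. It would be tempting to work out a likely number retreated per regimen and the share that one exclusion represents. The documents give no response, relapse or deviation rates for this. An even split over regimens would also be wrong: the 0.0048 mg/kg arm is half-size, and under Protocol 3.3 participants who relapse after the dose selection that follows the interim analysis receive the one selected regimen.

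The primary analysis does not use the RTS. The safety endpoint in Protocol Table 2-1 is limited to the Core Period, so no secondary safety endpoint is affected either.

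**What to change.** In the RTS row of Table 5-2, keep only the absence of any retreatment infusion as a reason for exclusion when the set is used for safety and exposure. That agrees with SAP 2.1.3 and with Protocol 12.1 and 12.5.2. Move the relapse and responder/remitter conditions to the one endpoint that needs them, response or remission after the first retreatment infusion. SAP 2.5.1 already derives that endpoint among relapsing participants who had responded or remitted at End of Core.

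If the narrower set is deliberate, SAP section 4 should record it as a departure from the protocol.

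The cost is a wording change. No new data are needed. The descriptive retreatment MADRS summaries in SAP 2.4.6 also use the RTS, so they would then include every infused participant; the SAP should say whether that is intended.
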